5.4.3.3 Abortions

A spontaneous abortion should be classified as a serious adverse event (as the Sponsor considers abortions to be medically significant), recorded on the Adverse Event eCRF, and reported to the Sponsor immediately (i.e., no more than 24 hours after learning of the event; see Section [5.4.2](#)).

If a therapeutic or elective abortion was performed because of an underlying maternal or embryofetal toxicity, the toxicity should be classified as a serious adverse event, recorded on the Adverse Event eCRF, and reported to the Sponsor immediately (i.e., no more than 24 hours after learning of the event; see Section [5.4.2](#)). A therapeutic or elective abortion performed for reasons other than an underlying maternal or embryofetal toxicity is not considered an adverse event.

All abortions should be reported as pregnancy outcomes on the paper Clinical Trial Pregnancy Reporting Form.

5.4.3.4 Congenital Anomalies/Birth Defects

Any congenital anomaly/birth defect in a child born to a female patient exposed to study drug or the female partner of a male patient exposed to study drug should be classified as a serious adverse event, recorded on the Adverse Event eCRF, and reported to the Sponsor immediately (i.e., no more than 24 hours after learning of the event; see Section [5.4.2](#)).

5.5 FOLLOW-UP OF PATIENTS AFTER ADVERSE EVENTS

5.5.1 Investigator Follow-Up

The investigator should follow each adverse event until the event has resolved to baseline grade or better, the event is assessed as stable by the investigator, the patient is lost to follow-up, or the patient withdraws consent. Every effort should be made to follow all serious adverse events considered to be related to study drug or trial-related procedures until a final outcome can be reported.

During the study period, resolution of adverse events (with dates) should be documented on the Adverse Event eCRF and in the patient's medical record to facilitate source data verification.

All pregnancies reported during the study should be followed until pregnancy outcome.

MSTT1041A/UTTR1147A—Genentech, Inc.
79/Protocol GA42469, Version 4

5.5.2 Sponsor Follow-Up

For serious adverse events, adverse events of special interest, and pregnancies, the Sponsor or a designee may follow up by telephone, fax, email, and/or a monitoring visit to obtain additional case details and outcome information (e.g., from hospital discharge summaries, consultant reports, autopsy reports) in order to perform an independent medical assessment of the reported case.

5.6 ADVERSE EVENTS THAT OCCUR AFTER THE ADVERSE EVENT REPORTING PERIOD

The Sponsor should be notified if the investigator becomes aware of any serious adverse event that occurs after the end of the adverse event reporting period (defined as the study completion/discontinuation visit), if the event is believed to be related to prior study drug treatment. These events should be reported through use of the Adverse Event eCRF. However, if the EDC system is not available, the investigator should report these events directly to the Sponsor or its designee, either by faxing or by scanning and emailing the paper Clinical Trial Serious Adverse Event/Adverse Event of Special Interest Reporting Form using the fax number or email address provided to investigators.

5.7 EXPEDITED REPORTING TO HEALTH AUTHORITIES, INVESTIGATORS, INSTITUTIONAL REVIEW BOARDS, AND ETHICS COMMITTEES

The Sponsor will promptly evaluate all serious adverse events and adverse events of special interest against cumulative product experience to identify and expeditiously communicate possible new safety findings to investigators, IRBs, ECs, and applicable health authorities based on applicable legislation.

To determine reporting requirements for single adverse event cases, the Sponsor will assess the expectedness of these events through use of the reference safety information in the documents listed below:

Drug	Document
MSTT1041A	RO7187807 Investigator's Brochure
UTTR1147A	RO7021610 Investigator's Brochure

The Sponsor will compare the severity of each event and the cumulative event frequency reported for the study with the severity and frequency reported in the applicable reference document.

Reporting requirements will also be based on the investigator's assessment of causality and seriousness, with allowance for upgrading by the Sponsor as needed.

A DMC will monitor the incidence of the above-listed anticipated events during the study. An aggregate report of any clinically relevant imbalances that do not favor the test product will be submitted to health authorities.

6. STATISTICAL CONSIDERATIONS AND ANALYSIS PLAN

Efficacy analyses will be conducted on the modified intent-to-treat (mITT) population. The mITT population is defined as all patients randomized in the study who received at least one dose of study drug, with patients grouped according to the treatment assigned at randomization.

Safety analyses will be conducted for the safety population, which consists of patients who received at least one dose of study drug, with patients grouped according to the treatment received.

6.1 DETERMINATION OF SAMPLE SIZE

A total of approximately 390 patients will be randomly allocated in a 2:2:1:1 ratio to receive MSTT1041A, UTTR1147A, or their matching placebos. The sample size provides approximately 80% power using a log-rank Chi-square test to detect a 7-day difference between treatment groups in time to *recovery*, *defined as time to score of 1 or 2 on the 7-category ordinal scale (whichever occurs first)*, under the following assumptions: median time to improvement in the placebo group is 21 days, with 28 days follow-up, and using a one-sided 5% alpha. The minimal detectable difference is expected to be approximately 5.3 days.

6.2 SUMMARIES OF CONDUCT OF STUDY

The number of patients who enroll, discontinue, or complete the study will be summarized by treatment group. Reasons for premature study discontinuation will be listed and summarized. Enrollment and major protocol deviations will be listed and summarized.

6.3 SUMMARIES OF DEMOGRAPHIC AND BASELINE CHARACTERISTICS

Demographic and baseline characteristics (including, but not limited to, age, sex, days from illness onset to randomization, geographic region, ordinal scale for clinical status, invasive mechanical ventilation) will be summarized using means, standard deviations, medians, and ranges for continuous variables and proportions for categorical variables, as appropriate. Summaries will be presented overall and by treatment group for the mITT and safety population.

6.4 EFFICACY ANALYSES

Efficacy analyses will be conducted on the mITT population, consisting of all patients randomized in the study who received at least one dose of study drug, with patients grouped according to the treatment assigned at randomization.

MSTT1041A/UTTR1147A—Genentech, Inc.
81/Protocol GA42469, Version 4

MSTT1041A placebo and UTTR1147A placebo will be pooled in efficacy analyses. Comparison of efficacy will be performed between each of the two treatment groups and the pooled placebo. That is, there are two comparisons:

- MSTT1041A with pooled placebo
- UTTR1147A with pooled placebo

Sensitivity analyses to evaluate the robustness of results will be conducted with comparison of primary efficacy endpoint between MSTT1041A and MSTT1041A placebo, and between UTTR1147A and UTTR1147A placebo.

Details on analysis methods, sensitivity analyses, hypothesis testing, and type I error control across treatment groups will be specified in the Data Analysis Plan (DAP).

Unless otherwise noted, analyses of efficacy outcome measures will be adjusted by stratification factors (the need for invasive mechanical ventilation [yes vs. no] and region).

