3.1.2 Data Monitoring Committee

A DMC will review unblinded safety and efficacy data to assess whether treatment with MSTT1041A or UTTR1147A is associated with toxicity or worsening disease. Members of the DMC will include representatives from Clinical Science and Drug Safety who are not directly involved in the study and representatives from Biostatistics and Statistical Programming and Analysis and may invite representatives from other functional areas on an ad-hoc basis when additional expertise is required (e.g., Clinical Pharmacology, Research). The DMC will also include at least two external experts in the field, and additional experts may be added during the course of the study.

The DMC will review cumulative safety data through at least Day 14 after the first 30 patients have been enrolled or after the first 30 days from the first patient enrolled (whichever occurs first). Subsequently, the DMC will review cumulative safety and efficacy data after each additional 75 patients have been enrolled or 3 months (whichever occurs first); for example, once *approximately* 75, 150, 225, and 300 patients have enrolled. Ad hoc meetings may be held at the request of the DMC or Sponsor at any time to address potential safety concerns. The DMC will have access to all available data at each review to perform an overall benefit/risk assessment. Data to be reviewed will include demographics, concomitant medications, study drug administration, ECGs, laboratory data, adverse events, serious adverse events, adverse events of special interest, and deaths.

MSTT1041A/UTTR1147A—Genentech, Inc.
36/Protocol GA42469, Version 4

At the time of each review, the DMC can make one of the following recommendations: the trial continues as planned, additional analyses need to be performed, enrollment is held pending further safety evaluations or other study modifications, the MSTT1041A or UTTR1147A arm of the trial is stopped, or the trial is stopped. Final decisions will rest with the Sponsor's study team.

Any outcomes of these reviews that affect study conduct will be communicated in a timely manner to the investigators for notification of their respective Institutional Review Board (IRB) or Ethics Committee (EC).

A detailed description of the procedures, data flow, and meeting schedule will be provided in the DMC Charter.

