4.2 METHOD OF TREATMENT ASSIGNMENT AND BLINDING

4.2.1 Treatment Assignment

This is a randomized, double-blind, placebo-controlled study. After initial written informed consent has been obtained, all screening procedures and assessments have been completed, and eligibility has been established for a patient, the study site will obtain the patient's identification number and treatment assignment from an interactive voice or web-based response system (IxRS).

MSTT1041A/UTTR1147A—Genentech, Inc.
45/Protocol GA42469, Version 4

Patients will be randomly assigned to one of four treatment arms: MSTT1041A, UTTR1147A, or their matching placebos. Randomization will occur in a 2:2:1:1 ratio through use of a permuted-block randomization method to ensure a balanced assignment to each treatment arm. Randomization will be stratified according to need for invasive mechanical ventilation (yes vs. no) and region. The proportion of patients with a need for invasive mechanical ventilation will be capped at approximately 25% of the overall study population.

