4.2.2 Blinding

Study site personnel and patients will be blinded to treatment assignment of MSTT1041A and UTTR1147A versus their respective placebos during the study. The Sponsor and its agents will also be blinded to treatment assignment of MSTT1041A and UTTR1147A versus their respective placebos, with the exception of IxRS service provider, and prespecified personnel (e.g., DMC members).

PK samples may be used to assess immunogenicity. While PK samples must be collected from patients assigned to the placebo arm to maintain the blinding of treatment assignment, PK and ADA assay results for these patients are generally not needed for the safe conduct or proper interpretation of the study data. Laboratories responsible for performing study drug PK and ADA assays will be unblinded to patient treatment assignments to identify appropriate samples for analysis. PK samples from patients assigned to the placebo arm will not be analyzed for study drug PK concentration except by request (e.g., to evaluate a possible error in dosing). Baseline ADA samples will be analyzed for all patients. Postbaseline ADA samples from patients assigned to the placebo arm will not be analyzed for ADAs except by request. Baseline and postbaseline samples will be collected for all patients.

If unblinding is necessary for a medical emergency (e.g., in the case of a serious adverse event for which patient management might be affected by knowledge of treatment assignment), the investigator will be able to break the treatment code by contacting the IxRS. The investigator is not required to contact the Medical Monitor prior to breaking the treatment code; however, the treatment code should not be broken except in emergency situations.

If the investigator wishes to know the identity of the study drug for any reason other than a medical emergency, he or she should contact the Medical Monitor directly.

As per health authority reporting requirements, the Sponsor's Drug Safety representative will break the treatment code for all serious, unexpected suspected adverse reactions (see Section 5.7) that are considered by the investigator or Sponsor to be related to study drug. The patient may continue to receive treatment, and the investigator, patient, and Sponsor personnel, with the exception of the Drug Safety representative and personnel who must have access to patient treatment assignments to fulfill their roles (as defined above), will remain blinded to treatment assignment.

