6.4.1 Primary Efficacy Endpoint

The primary efficacy objective for this study is to evaluate the efficacy of MSTT1041A compared with placebo and of UTTR1147A compared with placebo, in combination with SOC, on the basis of the following endpoint:

- *Time to recovery, defined as time to score of 1 or 2 on the 7-category ordinal scale (whichever occurs first)*

The ordinal scale categories are as follows:

1. Discharged (or “ready for discharge” as evidenced by normal body temperature and respiratory rate, and stable oxygen saturation on ambient air or ≤ 2 L supplemental oxygen)
2. Non-ICU hospital ward (or “ready for hospital ward”) not requiring supplemental oxygen
3. Non-ICU hospital ward (or “ready for hospital ward”) requiring supplemental oxygen
4. ICU or non-ICU hospital ward, requiring non-invasive ventilation or high-flow oxygen
5. ICU, requiring intubation and mechanical ventilation
6. ICU, requiring ECMO or mechanical ventilation and additional organ support (e.g., vasopressors, renal replacement therapy)
7. Death

Time to recovery will be analyzed using the stratified log-rank test, adjusting for stratification factors. The Kaplan-Meier plot, median time to event, and their 95% CI and p-value from the stratified log-rank test will be presented. A Cox proportional hazards regression model will be used to estimate the hazard ratio comparing MSTT1041A or UTTR1147A with placebo, respectively, adjusting for stratification

MSTT1041A/UTTR1147A—Genentech, Inc.
82/Protocol GA42469, Version 4

factors. Hazard ratios and 95% CIs will be presented. In addition, the *p*-value from unstratified log-rank test, unadjusted hazard ratio, and 95% CI will also be presented. Further details on the primary endpoint analysis will be included in the DAP.

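### If one drug arm and its matching placebo stop early, the pooled-placebo primary comparison needs an enrolment-period stratum

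*Protocol*

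**What the plan says.** Section 4.2.1: "Randomization will occur in a 2:2:1:1 ratio through use of a permuted-block randomization method". Blinding in Section 4.2.2 is within each drug and placebo pair: patients and site staff are "blinded to treatment assignment of MSTT1041A and UTTR1147A versus their respective placebos during the study".

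Section 6.4: "MSTT1041A placebo and UTTR1147A placebo will be pooled in efficacy analyses", and each drug is compared with that pooled group. Unless otherwise noted, efficacy analyses are "adjusted by stratification factors (the need for invasive mechanical ventilation [yes vs. no] and region". Section 6.4.1 applies this to the primary endpoint: "Time to recovery will be analyzed using the stratified log-rank test, adjusting for stratification factors". Neither section limits the pool to patients randomised concurrently. Section 6.4 also plans a sensitivity analysis of the primary endpoint "between MSTT1041A and MSTT1041A placebo, and between UTTR1147A and UTTR1147A placebo", and leaves further detail to the Data Analysis Plan (DAP).

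Section 3.1.2 lists among the possible DMC recommendations that "the MSTT1041A or UTTR1147A arm of the trial is stopped, or the trial is stopped", with reviews when, for example, about "75, 150, 225, and 300 patients have enrolled". Section 1.4.2 also names discontinuation of a treatment arm as a possible recommendation.

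**The concern.** While all four arms enrol, two patients go to each drug for every two on the pooled placebos, so each comparison is 1:1 in every period and pooling does no harm. If one drug and its placebo close, the remainder of 2:2:1:1 is 2:1. The surviving drug's share of its comparison rises from 1/2 to 2/3, and treatment becomes associated with time of enrolment. Neither stated stratum removes that association.

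Recovery could plausibly change over the expected study length of about 10 months. Section 3.1.1 leaves standard of care to the site, and Section 3.3.4 describes antiviral and host-directed therapies as experimental. Faster recovery in the later period would make the surviving drug look effective when it is not. Slower recovery would hide a real effect.

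**Working it through.** **The plan's own figure.** Section 6.1 gives 390 patients, a placebo median of 21 days, a 7-day difference (14 against 21 days, so HR 1.5 if times are exponential), 28 days of follow-up, one-sided 5% alpha and about 80% power.
- Recovered by Day 28: placebo 1 − 2^(−28/21) = 0.603; active 1 − 2^(−28/14) = 0.750.
- Events at 130 against 130: 130 × (0.603 + 0.750) = 175.9.
- Schoenfeld power: Φ(√(175.9/4) × ln 1.5 − 1.645) = 85.2%.
- With 10% or 15% fewer events: 81.7% or 79.8%.

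The stated figure is therefore attainable with modest loss and is not in dispute. The same formula for one drug against its own placebo (130 against 65) gives 72.2%.

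**The example.** Three things are assumed: UTTR1147A stops at 150 enrolled, its placebo stops with it, and MSTT1041A continues 2:1 until it has 130 patients.
- Before the stop: 150 × 2/6 = 50 on the surviving drug and 150 × (1 + 1)/6 = 50 on pooled placebo.
- After the stop: 80 on drug and 40 on placebo.
- Total: 130 against 90. Late patients are 80/130 = 62% of the drug group and 40/90 = 44% of the placebo group.

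**Direction, by hand.** Suppose the drug does nothing and the recovery hazard rises 1.5-fold after the stop (median from 21 to 14 days). Expected recovery by Day 28 is then:
- drug: (50 × 0.603 + 80 × 0.750)/130 = 69.3%
- placebo: (50 × 0.603 + 40 × 0.750)/90 = 66.8%

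The gap of about 2.5 points comes only from the mix of periods.

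**Size of the test.** This was simulated under no drug effect, with exponential times censored at Day 28 and a one-sided 5% log-rank test. Ventilation and region were left out because they carry no calendar information in this model.

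| Rise in recovery hazard | Pooled, abrupt at the stop | Pooled, same change spread evenly over enrolment |
|---|---|---|
| 1.25 times | about 7-8% | about 6% |
| 1.5 times | about 10-11% | about 7% |
| 2 times | about 16-17% | about 9-10% |

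With enrolment period as a stratum, size was 4.2% to 5.6% across the scenarios run. The own-placebo comparison, which is 2:1 in both periods, gave 3.8% to 5.7%. Monte Carlo error is about 0.3 to 0.5 points.

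**Other stopping points and completion rules.** Stops at about 150, 225 and 300 were run, with enrolment ending either at 130 on the surviving drug or at 390 in total.
- An abrupt fall in median recovery from 21 to 18 days: size 6.3% to 7.4%.
- An abrupt fall from 21 to 14 days: size 7.9% to 12.5%, mean hazard ratio 1.04 to 1.07.
- A steady 21-to-14-day trend: size 6.3% to 8.3%, mean hazard ratio 1.02 to 1.04.

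**Power.** In the example, with a true HR of 1.5 and a later hazard 0.67 times the earlier one, power is about 59% pooled and about 73% with a period stratum. With no trend it is about 76-78% pooled and 75-76% stratified. Own-placebo power in the example was 65% to 69%.

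**Check on the mechanism.** If both placebos kept enrolling, so that allocation stayed 1:1, a 21-to-14-day step gave 4.7% size and a mean hazard ratio of 1.00. The bias comes from the change in allocation, not from pooling as such.

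**The case against.** The strongest objection is that this belongs in the DAP. Section 6.4 defers analysis details and type I error control to it, the adjustment set is qualified by an unless-otherwise-noted clause, and nothing is wrong while all arms enrol. Closing an arm would also change the randomisation and might well prompt an amendment in which a stratum could be added. Part of this stands: the problem is conditional and could still be dealt with later. But the protocol already names the control group and the adjustment factors, and a DAP that followed them literally after a stop would give a biased primary comparison. Fixing the rule beforehand also avoids choosing it after unblinded reviews.

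A second objection is that Section 6.4 already has a safeguard. It does. A reader might infer from the pooling rule that the protocol offers no protection against drift, and that would be wrong: the own-placebo sensitivity analysis is unaffected and would allow a pooled result to be checked. It is not the primary analysis, however, it has less power, and nothing says which result prevails if the two disagree.

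Two other readings also go too far. A reader might take 2:1 after a stop as the protocol's rule, but no post-stop ratio is stated; it is inferred because a placebo whose drug had closed would be recognisable as placebo. A reader might also infer that any calendar trend causes bias. The trend must make recovery differ between the two periods, beyond what ventilation and region explain.

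**Conclusion.** The point holds in conditional form and is a cheap improvement, not a defect of the design while all arms are open. It needs one drug to be stopped (a DMC recommendation, with the final decision resting with the sponsor's study team), the other to continue, the stopped drug's placebo to close too, and recovery to differ between the periods. Given those conditions, the surviving primary comparison is biased, towards the drug if recovery speeds up and against it if recovery slows.

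The documents give no trend, so all trend sizes are assumptions. The abrupt-jump figures are the unfavourable end: a doubled hazard means the median falling from 21 to 10.5 days at the stop. Gradual change gives a smaller inflation. Exponential recovery times are also assumed.

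**What to change.** Add to Sections 6.4 and 6.4.1, and carry into the DAP: if an arm is stopped early and allocation against pooled placebo changes, enrolment period (before or after the stop) is added as a stratum to the log-rank test and the Cox model of the remaining comparison, so that drug and placebo patients are compared within period. The pooled control and the own-placebo sensitivity analysis stay as they are.

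The cost is one sentence in each place and about 1 point of power when there is no trend. If both arms run to completion the rule never applies and nothing changes.

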6.4.1 Primary Efficacy Endpoint

The primary efficacy objective for this study is to evaluate the efficacy of MSTT1041A compared with placebo and of UTTR1147A compared with placebo, in combination with SOC, on the basis of the following endpoint:

- *Time to recovery, defined as time to score of 1 or 2 on the 7-category ordinal scale (whichever occurs first)*

The ordinal scale categories are as follows:

1. Discharged (or “ready for discharge” as evidenced by normal body temperature and respiratory rate, and stable oxygen saturation on ambient air or ≤ 2 L supplemental oxygen)
2. Non-ICU hospital ward (or “ready for hospital ward”) not requiring supplemental oxygen
3. Non-ICU hospital ward (or “ready for hospital ward”) requiring supplemental oxygen
4. ICU or non-ICU hospital ward, requiring non-invasive ventilation or high-flow oxygen
5. ICU, requiring intubation and mechanical ventilation
6. ICU, requiring ECMO or mechanical ventilation and additional organ support (e.g., vasopressors, renal replacement therapy)
7. Death

Time to recovery will be analyzed using the stratified log-rank test, adjusting for stratification factors. The Kaplan-Meier plot, median time to event, and their 95% CI and p-value from the stratified log-rank test will be presented. A Cox proportional hazards regression model will be used to estimate the hazard ratio comparing MSTT1041A or UTTR1147A with placebo, respectively, adjusting for stratification

MSTT1041A/UTTR1147A—Genentech, Inc.
82/Protocol GA42469, Version 4

factors. Hazard ratios and 95% CIs will be presented. In addition, the *p*-value from unstratified log-rank test, unadjusted hazard ratio, and 95% CI will also be presented. Further details on the primary endpoint analysis will be included in the DAP.

